## 8.7 Randomization and Blinding

This is an open-label study and there is no randomization or blinding.

## 8.8 Prior and Concomitant Medications

Please see exclusion criteria for prohibited medications.

Concomitant medications are any prescription or over-the-counter preparations used from 2 days prior to the preparatory regimen before Day 0 through the end of the subject's study participation.

Standard myeloablative preparatory regimens, (i.e., reduced intensity conditioning, non myeloablative conditioning, experimental regimens or drugs are not allowed), HSCT and standard supportive care/ prophylactic treatments (including but not limited to colony stimulating factors, transfusions, antibiotics/anti-virals/anti-fungals) per institutional guidelines for optimal medical care shall be permitted during participation of this study. The dose of steroids that are required for reasons unrelated to the underlying malignancy or HSCT process or sequelae must not be higher than physiologic doses (the equivalent of 20 mg/day of prednisone). No anti-thymocyte globulin (ATG) is allowed in the conditioning regimen.

GvHD prophylaxis must consist of a calcineurin inhibitor (cyclosporine or tacrolimus) in combination with MTX or MMF. Dosing, schedule and monitoring of the GvHD regimen should follow institutional guidelines. Please see respective prescribing information for safety information. Steroids, sirolimus, post-transplant cyclophosphamide, ATG, other GvHD

prophylactic agents (including investigational agents) or manipulation of the graft to reduce GvHD are not allowed.

Post transplant maintenance therapy that includes an investigational agent, or any treatments that can be used for GvHD are not allowed. Maintenance therapy for actionable targeted mutations (e.g., FLT3 inhibitors) or with FDA approved agents in any indication should not be initiated prior to Day 42 post alloHSCT.

Treatment of GvHD should follow institutional guidelines and may include steroid treatment at supra-physiologic doses. See [Section 7.5.3](#) for development of GVHD prior to completion of RGI-001 dosing.

The investigator may prescribe additional medications during the study, as long as the prescribed medication is not prohibited by the protocol. In the event of an emergency, any needed medications may be prescribed without prior approval, but the Medical Monitor must be notified of the use of any medications, except acetaminophen, immediately after use. Any concomitant medications added or discontinued during the study should be recorded on the electronic case report form (eCRF.)

## **8.9 Dietary or Other Protocol Restrictions**

Dietary restrictions per institutional guidelines (e.g. neutropenic diet) may be imposed on study subjects. Alcohol and tobacco use should be limited as per institutional guidelines.

## **8.10 Dose Modification/Treatment Cessation**

If a subject permanently discontinues treatment in the Safety Run-in or Expansion Phase as specified below, see [Section 7.5.3](#) Discontinuation of Study Treatment and/or Withdrawal of Subjects Prior to Study Completion, for further details.

### ***8.10.1 Safety Run-in Phase***

RGI-2001 will be administered at a dose of 100 µg/kg IV weekly for 6 doses. There are no dose reductions or escalations in this portion of the study except as recommended by the SRC at the end of the run-in period. Each individual infusion is allowed to be delayed up to 2 weeks for ongoing grade 3+ AEs, regardless of causality. However, if a subject enrolled in the run-in period is not able to receive at least 50% of RGI-2001 doses during the DLT window for reasons other than toxicity, then that subject will be replaced. Subjects requiring delay of an infusion of > 2 weeks should be discontinued from treatment.

Subjects enrolled in the Run-in Phase beyond the DLT window who meet DLT criteria should be discontinued from study treatment. Supportive care should be administered as appropriate.

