### 6.1.1 Definition of Dose-limiting Toxicities

[figure not shown]
All subjects are expected to experience hematologic toxicity as part of the myeloablative alloHSCT procedure. Therefore, hematologic toxicities (e.g., leukopenia and thrombocytopenia) will not be useful measures of drug-induced toxicity, and DLTs are defined by non-hematologic toxicities.

The following DLT criteria apply to the Safety Run-in Phase of the study. A DLT is defined as any treatment-related AE that is not attributable to an extraneous cause (i.e., disease progression, preparatory regimen or HSCT infusion) and also excludes any signs and symptoms of GvHD. DLT is an adverse event occurring in the period of 30 days after the first dose of RGI-2001 administration, and meeting at least one of the following NCI CTC (Version 5.0) criteria:

- Grade 3+ infusion-related/cytokine release reactions
- Graft failure (as defined in Section 9.4.1.)
- Any Grade 4-5 non-hematological AE
- Delay in dosing by > 2 weeks due to treatment-related AE that is not attributable to an extraneous cause as defined above

Subjects who do not complete the DLT window for reasons other than toxicity may be replaced. Similarly, if a subject receives ≤ 50% of planned doses of RGI-2001 for reasons other than toxicity considered related to RGI-2001, this subject may be replaced.

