### ***8.10.2 Expansion Phase***

RGI-2001 will be administered at the dose and schedule agreed upon by the SRC at the completion of the Safety Run-In Phase. No dose escalations will be allowed.

If a subject has a treatment related Grade 3 adverse event (excluding any hematologic AE or CRS) that is not considered to be related to extraneous cause ((i.e. disease progression, preparatory regimen, HSCT infusion), subsequent doses will be held until the toxicity returns to  $\leq$  Grade 2 or baseline. RGI-2001 may be restarted at a dose of 10  $\mu$ g/kg IV infusion.

Subjects who meet DLT criteria (including Grade 3+ CRS) at any point in the study should be permanently discontinued from study treatment. Supportive care should be administered as appropriate.

If subject has a 2nd occurrence of Grade 3 adverse event, RGI-2001 will be held until the toxicity returns to  $\leq$  Grade 2 or baseline. RGI-2001 will be restarted at a dose of 1  $\mu$ g/kg IV infusion.

If a subject experiences a Grade 4 adverse event that is related or continues to have recurrence of Grade 3 adverse events beyond the 2nd instance, discontinue RGI-2001 permanently.

If a subject does not demonstrate evidence of myeloid engraftment by Day 28, discontinue RGI-2001 permanently.

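### Protocol 8.10.1 states no mandatory stop for a related grade 4 DLT inside the run-in window, and it is unclear whether the stop under the expansion heading covers it

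*Protocol*

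**What the plan says.** Protocol 8.10.1 governs dosing of the individual subject in the run-in. It contains four relevant provisions:

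- Dose level: "There are no dose reductions or escalations in this portion of the study except as recommended by the SRC", with that recommendation placed at the end of the run-in.
- Holds: "Each individual infusion is allowed to be delayed up to 2 weeks for ongoing grade 3+ AEs, regardless of causality".
- Stop for long delay: "Subjects requiring delay of an infusion of > 2 weeks should be discontinued from treatment".
- Stop for DLT: "Subjects enrolled in the Run-in Phase beyond the DLT window who meet DLT criteria should be discontinued from study treatment".

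Protocol 6.1.1 defines a DLT as a treatment-related AE, without an extraneous cause and excluding signs of GvHD, that occurs within 30 days of the first dose and meets a listed criterion. One criterion is "Any Grade 4-5 non-hematological AE". The section introduces the list with "The following DLT criteria apply to the Safety Run-in Phase of the study".

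Protocol 8.10.2, headed Expansion Phase, says: "Subjects who meet DLT criteria (including Grade 3+ CRS) at any point in the study should be permanently discontinued from study treatment". It also requires permanent discontinuation for a related grade 4 AE and for no evidence of myeloid engraftment by Day 28. Section 7.5.3 lists AEs of the DLT type among the reasons for removal, but as a decision open to the investigator or sponsor.

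**The concern.** The DLT stop in 8.10.1 applies after the window, whereas 6.1.1 places DLTs within it. Taken alone, the run-in rule omits the 30 days in which a DLT is defined to occur. Because holds are allowed for grade 3 and above and the dose may not be lowered, any dose resumed after such an event would be at the full 100 µg/kg.

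Subject safety is at stake more than the DLT count, since the event already counts towards the cohort decision in 6.1. The earlier study gave a single infusion (4.5), so this run-in is the first test of repeat dosing. A site that applies 8.10.1 literally and a site that applies 8.10.2 to all subjects could handle the same event differently within a cohort of 3. One of those readings would re-expose the subject.

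**Working it through.** This is mainly a comparison of texts. The plan gives no figure to reproduce.

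**Step 1. Which doses lie inside the window.** Planned dosing days are 0, 7, 14, 21, 28 and 35 (6.1), and the window is 30 days (6.1.1). Days 0, 7, 14, 21 and 28 are all ≤ 30, so 5 of 6 planned doses fall inside. Day 35 falls outside. Four follow-on doses (Days 7 to 28) are therefore planned within the window.

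**Step 2. Worked case.** A related, non-hematological, non-cytokine grade 4 AE starts on Day 10. The next infusion is due on Day 14. With the longest permitted hold, it is given on Day 14 + 14 = Day 28, which is ≤ 30. Neither stop in 8.10.1 has been triggered: the delay does not exceed 2 weeks, and the subject is not past the window.

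**Step 3. Which in-window events already have a mandatory stop.**

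| Run-in event inside the window | Mandatory stop |
|---|---|
| Grade 3-4 cytokine or infusion reaction | Yes: 8.11 and Table 1, not limited by phase |
| Any AE delaying an infusion by more than 2 weeks | Yes: 8.10.1 |
| Grade 5 event | Moot |
| Hematologic grade 4 AE | Not a DLT under 6.1.1 |
| No myeloid engraftment by Day 28 | Stated only in 8.10.2; largely overlaps the graft-failure DLT (6.1.1, defined in 9.4.1) |
| Related, non-hematological, non-cytokine grade 4 AE, delay of 2 weeks or less | None in 8.10.1; possibly 8.10.2 |

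The gap is the last row. The engraftment row concerns at most one in-window dose, on Day 28.

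**Step 4. Whether 8.10.2 clearly covers the last row.** Four features point away from it:

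- It sits under the Expansion Phase heading, and 8.10 introduces the rules of both phases with "If a subject permanently discontinues treatment in the Safety Run-in or Expansion Phase as specified below", which suggests each phase has its own.
- Its neighbouring restarts at 10 and 1 µg/kg conflict with the ban on reductions in 8.10.1, so 8.10.2 cannot apply wholesale to the run-in.
- If its DLT sentence did reach run-in subjects, the DLT sentence in 8.10.1 would be redundant.
- Its wording on timing may serve only to lift the 30-day limit when the run-in criteria are borrowed for expansion.

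**Step 5. Whether anything else must happen before the next weekly dose.** A related grade 4 AE would ordinarily be an SAE, reported within 24 hours (10.3.1), and the SRC monitors safety on an ongoing basis (6.4). Neither provision requires a stop or a sign-off. The scheduled SRC review comes after the third subject reaches Day 30 (6.1). The protocol does state a Medical Monitor check before further dosing after acute GvHD (7.5.3) and after a cytokine reaction (8.11), but states none here.

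**The case against.** The strongest reply is that 8.10.2 already settles the matter. It applies to anyone meeting DLT criteria at any time in the study, and 6.1.1 says those criteria belong to the run-in. A rule built on run-in criteria and worded for the whole study naturally includes run-in subjects. On that view 8.10.1 only extends the stop past Day 30 and takes the in-window stop for granted. The alternative would stop a subject for an event on Day 33 but not for the same event on Day 10, which nobody would choose. The hold clause can also be read as a timing allowance for the any-cause toxicity expected after myeloablative transplant.

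Much of this stands. It makes the intent clear enough, and the protocol as a whole is not silent. It does not remove the conflict of headings and doses in step 4, and a stopping rule for life-threatening events should not depend on inference.

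Three stronger readings are tempting, and the documents support none of them:

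- A reader might infer that the protocol permits or directs re-dosing at 100 µg/kg after a DLT. It does neither. Section 8.10.1 alone fails to exclude it, and 8.10.2 plausibly does exclude it.
- A reader might estimate a frequency from the single-dose study, where 4.6 mentions grade 4 TEAEs in two subjects at 100 µg/kg. Those cases were sepsis, and septic shock with respiratory failure. Their relatedness is not stated, the list may be incomplete, and the number treated at that dose in Part 1 is not given. They do not measure the related, non-cytokine event at issue.
- A reader might compute exactly how many re-doses are possible. That needs a rule for how a held dose moves the later ones, and the protocol gives none. Only the planned count in step 1 is secure.

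**Conclusion.** The concern holds as an ambiguity in a safety rule. The run-in section states no mandatory stop for an in-window, treatment-related, non-hematological, non-cytokine grade 4 AE that resolves within 2 weeks. The only mandatory stop that could apply is placed under the other phase, and 7.5.3 is discretionary.

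The size is small in numbers: about 6 run-in subjects per dose, with 5 of 6 planned doses inside the window. How often the event would occur cannot be stated from the documents. The likely intent is that any DLT ends dosing, and many investigators would stop anyway. I rate this a should-fix safety clarification.

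The conclusion assumes that neither Figure 2 (the DLT schema, not shown) nor the SRC charter (not provided) already states the in-window stop. SAP 3.0 reports in the past tense that no subject met a replacement criterion, so the run-in may be complete. If so, the useful step is to confirm how any in-window DLT was handled.

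**What to change.** In Protocol 8.10.1:

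1. Reword the DLT sentence so that any run-in subject who meets a DLT criterion, whether during or after the 30-day window, permanently stops RGI-2001. Deleting the four words *beyond the DLT window* achieves the core of this.
2. Add that the 2-week hold is not available for an AE that meets a DLT criterion.
3. Optionally, repeat the Day 28 no-engraftment stop from 8.10.2. It largely overlaps the graft-failure DLT, so little is lost without it.

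The cost is one sentence replaced and one added (two with the optional item), with no extra visits, procedures or subjects. The downside is that a run-in subject whose related grade 4 AE has resolved loses the remaining doses, as already applies in expansion.

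If the run-in is over, compare the DLT listing (SAP Listing 16.2.7.3) with the infusion listing (16.2.5.3) and report whether any subject was dosed after an in-window DLT.

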### ***8.10.2 Expansion Phase***

RGI-2001 will be administered at the dose and schedule agreed upon by the SRC at the completion of the Safety Run-In Phase. No dose escalations will be allowed.

If a subject has a treatment related Grade 3 adverse event (excluding any hematologic AE or CRS) that is not considered to be related to extraneous cause ((i.e. disease progression, preparatory regimen, HSCT infusion), subsequent doses will be held until the toxicity returns to  $\leq$  Grade 2 or baseline. RGI-2001 may be restarted at a dose of 10  $\mu$ g/kg IV infusion.

Subjects who meet DLT criteria (including Grade 3+ CRS) at any point in the study should be permanently discontinued from study treatment. Supportive care should be administered as appropriate.

If subject has a 2nd occurrence of Grade 3 adverse event, RGI-2001 will be held until the toxicity returns to  $\leq$  Grade 2 or baseline. RGI-2001 will be restarted at a dose of 1  $\mu$ g/kg IV infusion.

If a subject experiences a Grade 4 adverse event that is related or continues to have recurrence of Grade 3 adverse events beyond the 2nd instance, discontinue RGI-2001 permanently.

If a subject does not demonstrate evidence of myeloid engraftment by Day 28, discontinue RGI-2001 permanently.

### 8.11 Management of Cytokine Release Syndrome

Pre-medications for RGI-2001 will not be administered initially as no signs of cytokine release were observed in the Phase 1 study. If symptoms suggestive of cytokine release (fever, chills, etc.) are observed with administration of RGI-2001, subjects should be treated according to institutional guidelines. The SRC may provide additional recommendations for such situations (please refer to [Section 6.4](#)). For Grade 2 AEs, acetaminophen, diphenhydramine and/or steroids may be administered. Premedication for subsequent RGI-2001 infusions may consist of intravenous or oral dexamethasone (4 mg), acetaminophen and diphenhydramine prior to each administration of RGI-2001. Details should be discussed with the Medical Monitor prior to the next infusion. For subjects with Grade 3–4 infusion reaction/cytokine release symptoms should be discontinued from further RGI-2001 therapy regardless of whether prophylactic treatment was administered.

**Table 1 Medical Guidelines for Cytokine Release Reactions**

Grade 1	
 
Continue to monitor subject carefully.
 
No treatment is needed unless symptoms worsen
 
Consider pre-medications for subsequent infusions depending on the presentation.
 

Grade 2	
 
Hold infusion until symptoms resolve.
 
Supportive care as per institutional guidelines. May include but not limited to acetaminophen, diphenhydramine, H2 blockers, dexamethasone or equivalent, oxygen, demerol or equivalent, IV fluids, anti-emetics
 
For subsequent RGI-2001 infusions, premedicate with acetaminophen, diphenhydramine, dexamethasone 4mg or equivalent
 

Grade 3-4

- Discontinue RGI-2001 treatment
- Supportive care as per institutional guidelines. May include but not limited to acetaminophen, diphenhydramine, H2 blockers, dexamethasone or equivalent, oxygen, demerol or equivalent, IV fluids, anti-emetics, vasopressors, mechanical ventilation.

## 9 STUDY ASSESSMENTS AND PROCEDURES

The Schedule of Assessments in [Section 3](#) describes the frequency and timing of the study assessments and procedures. The schedule of PK and PD sample collection is provided in [Appendix 1](#). All enrolled subjects will undergo the same study procedures unless otherwise noted.

All screening evaluations must be completed and reviewed to confirm a potential subject meets all eligibility criteria prior to alloHSCT, including the preparatory regimen. Investigators are to maintain a screening log of all potential subjects.

Screening assessments must be performed within 14 days prior to initiation of any treatments related to the HSCT including the preparatory regimen unless otherwise specified. Informed consent, screening hepatitis, HIV tests, and tumor assessment (provided that no intervening therapy for their malignancy has been administered) may be obtained up to 42 days before the preparatory regimen. PFTs and ECHO may be obtained as per institutional standard of care criteria within 84 days prior to the preparatory regimen provided no intervening therapy for their malignancy has been administered. Pregnancy test must be conducted within 7 days before preparatory regimen. Standard of care tests/procedures, performed prior to the subject signing the informed consent form (ICF) can be used as part of the screening assessments as long as the tests/procedures are performed within the appropriate screening window. Screening assessments do not need to be repeated due to minor delays in procurement of donor HSC's.

### 9.1 General Study Procedures

#### 9.1.1 *Informed Consent*

Except as noted in [Section 9](#), informed consent must be obtained before conducting any study-specific activities/procedures and documented in the subject's source documents.

#### 9.1.2 *Demographics*

Subject demographics (including date/year of birth, sex, race, ethnicity, and age at the time of consent) will be collected.

#### 9.1.3 *Medical/Cancer/Surgical History*

A complete medical, cancer and surgical history starting prior to enrollment through the time of consent will be obtained from each subject at the Screening visit.

Prior cancer history includes: (i) date of diagnosis, (ii) prognostic score if applicable (iii) all previous therapies (i.e., chemotherapy, immunotherapy, biologic or targeted agents, experimental therapies, radiotherapy, and surgery), (iv) previous therapy details (i.e., regimen, start and stop dates), (v) best response for each regimen

Data from SOC procedures will be part of the subject's medical history and may be used for study purposes.

## 9.4 Safety Assessments

Safety will be assessed by clinical laboratory studies, time to myeloid and platelet engraftment and by monitoring of AEs.

Potential safety issues associated with the route of administration or the pharmacology of RGI-2001 include hypersensitivity to RGI-2001, organomegaly, microgranuloma, and infections. Subjects will be monitored closely for hypersensitivity reactions to RGI-2001. Infections will be recorded throughout the study. Subjects will be followed for 30 days following end of treatment and monitored for the occurrence of adverse events by means of physical examination, and laboratory testing, including hematology, T-cell, immunophenotyping, other serum chemistry, urinalysis and liver function tests.

### 9.4.1 Marrow Engraftment and Graft Failure

Myeloid engraftment will be defined as the first of 3 consecutive days when the absolute neutrophil counts (ANC) exceeds  $0.5 \times 10^9/L$  and platelet engraftment will be defined as the first of 3 consecutive days when the platelet count exceeds  $20 \times 10^9/L$  without transfusion support. Graft failure will be defined as the lack of myeloid engraftment in subjects surviving in remission for at least 28 days after transplantation.

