## 2 PROTOCOL SYNOPSIS

Name of Sponsor	REGiMMUNE Corporation (JAPAN) [name]
Protocol Title	An Open Label, Non-Randomized Multicenter Phase 2b, Study with a Safety Run-in to Evaluate the Safety and Efficacy of RGI-2001 for the Prevention of Acute Graft- Versus-Host Disease Compared to Contemporary Controls in Subjects Following Allogeneic Hematopoietic Stem Cell Transplantation (alloHSCT)
Name of Investigational Product	RGI-2001
Protocol Number	RGI-2001-003
Phase	Phase 2
Indication	Prevention of Acute Graft-versus-Host Disease following alloHSCT
Study Centers	This study will be conducted at 8-12 sites in the United States.
Study Rationale:	Despite efforts to date, the incidence of acute GvHD remains high. Thus, improvements in the prevention of the disease constitutes a high unmet medical need.  Studies in both humans and mice have confirmed the pivotal role CD4+Foxp3+ Treg cells play in controlling GvHD ( Socié 2009 ). However, the development of Treg cell-based therapeutic modalities has been hampered, in part, by the small numbers of these cells. RGI-2001 is a liposomal form designed to deliver RGI-7000, which is an immunomodulatory compound that may promote the proliferation of Tregs in donor bone marrow and the development of tolerance to alloantigens and therefore constitutes a novel approach to the prevention of GvHD.
Objectives	Endpoints
Primary	

 
To assess the potential efficacy of RGI-2001 in addition to standard of care (SOC) vs SOC for the prevention of acute GvHD (aGvHD)
 
To characterize the safety and tolerability of 6 weekly intravenous (IV) infusions of
 
	
 
Efficacy: Grades II-IV aGvHD by Day 100 according to the Modified Keystone Criteria (Przepiorka 1995)
 
Safety: Incidence, nature, and severity of treatment-emergent AEs, SAEs, laboratory test values, vital-sign measures, and graft failure
 

RGI-2001 in subjects following alloHSCT
	

Secondary
	

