- q Evaluation of status of hematologic malignancy should be conducted as per institutional guidelines but should include a bone marrow aspirate and biopsy with cytogenetics, molecular diagnostics and chimerism as appropriate based on disease histology at baseline, and at time intervals close to Days 100, 180 and 365.

- r Adverse events (AEs) must be recorded using National Cancer Institute (NCI) Common Terminology Criteria for Adverse Events (CTCAE v. 5.0) where possible. The reporting period for non-serious AEs starts after the first administration of study drug on Day 0. The reporting period for serious AEs starts after the informed consent form (ICF) has been signed. Adverse event monitoring should be continued for at least 30 days following the last dose of study drug. Infections should be recorded throughout the study. See [Section 10](#) for further details.
- s Review of all medications, including over-the-counter (OTC) preparations and herbal products. Concomitant medications used from 2 days prior to the preparatory regimen before Day 0 through the end of the subject's study participation, should be recorded. Maintenance therapy should be documented as a concomitant medication.

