## 7 SUBJECT POPULATION

### 7.1 Inclusion Criteria

All subjects (including CIBMTR control group, except where noted) must meet the following criteria:

1. Ages  $> 18$  and  $\leq 65$  years of age
2. Has a hematologic malignancy as defined below and is considered a candidate for allo HSCT:
  - a. Acute myelogenous leukemia (AML) in first or subsequent morphologic complete remission
  - b. T or B cell acute lymphoblastic leukemia (ALL) in first or subsequent complete morphologic remission
  - c. Myelodysplastic syndrome (MDS), chronic myelomonocytic leukemia (CMML), myeloproliferative disorder (MPD) including myeloid metaplasia and myelofibrosis and are currently with  $< 10\%$  blasts in bone marrow
  - d. CML subjects who have received prior treatment including at least one tyrosine kinase inhibitor and are currently in chronic phase or with a complete hematologic remission but with evidence of cytogenetic or molecular relapse
3. Must have adequate organ function as defined below (RGI-2001 treatment group only):
  - a. Cardiac function: Left ventricular ejection fraction at rest  $\geq 45\%$
  - b. Liver function: total bilirubin  $< 1.5$  x upper limit of normal (ULN); alanine aminotransferase (ALT) and aspartate aminotransferase (AST)  $< 2.5$  x the ULN. Patients who have been diagnosed with Gilbert's Disease or malignant involvement are allowed to exceed the defined bilirubin value of  $1.5$  x the ULN
  - c. Serum creatinine  $< 2$  mg/dL or estimated creatinine clearance  $> 50$  mL/min calculated using the Cockcroft-Gault equation
  - d. Pulmonary: DLCO (corrected for hemoglobin) and/or FEV1  $\geq 50\%$
4. Considered suitable candidate for a myeloablative allogeneic or unrelated donor transplant based on institutional criteria
5. Subject must be receiving first allogeneic transplant from a single donor. Prior autologous transplant is acceptable
6. Transplant Donor:
  - a. Matched related donor (8/8): Molecular identity at HLA-A, -B, -C and -DRB1 by high-resolution typing
  - b. Unrelated donor ( $\geq 7/8$  allelic match): high resolution molecular typing at the following loci is required HLA -A, -B, -C and -DRB1
  - c. Meets institutional criteria for bone marrow or PBSC donation (see [Section 7.4](#))

7. Source of the Allograft:
  - a. Unmodified bone marrow or mobilized peripheral blood stem cell (PBSC) transplant, using granulocyte colony stimulating factor (G-CSF) as the mobilizing agent. Cord blood is not allowed

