**Table 3 Suspension Rules for Grade 4-5 RRT, Graft Failure, and Day-100 NRM**

Safety outcome	Occurrences that would trigger suspension rule and SRC review
Day 30 grade 4-5 RRT	3 RRT of first 3 pts, 4 RRT of first 5 or fewer pts, 5/6, 6/7-8, 7/9-10, 8/11-12, 9/13, 10/14-15, 11/16-17, 12/18-19, 13/20-21, 14/22, 15/23-24, 16/25-26, 17/27-28, 18/29-30, 19/31-32, 20/33-34, 21/35, 22/36-37, 23/38-39, 24/40-41, 25/42-43, 26/44-45, 27/46-47, 28/48-49, 29/50
Graft Failure	2 failures of first 16 pts or fewer, 3/17-30, 4/31-46, 5/47-50
Day-100 NRM	2 failures of first 8 pts or fewer, 3/9-15, 4/16-23, 5/24-31, 6/32-39, 7/40-47, 8/48-50

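### Graft failure is defined only for subjects surviving in remission, yet some eligible diagnoses need not be in remission, so a true non-engraftment can fall outside the safety endpoint and the 5% suspension count

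*Protocol*

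**What the plan says.** Protocol Section 9.4.1 gives the definition: "Graft failure will be defined as the lack of myeloid engraftment in subjects surviving in remission for at least 28 days after transplantation". Three parts of the plan depend on it.

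- **Primary safety endpoint.** The synopsis lists "Safety: Incidence, nature, and severity of treatment-emergent AEs, SAEs, laboratory test values, vital-sign measures, and graft failure". Protocol Section 5 and SAP Section 1.1 repeat this.
- **Run-in DLT criteria.** Section 6.1.1 includes "Graft failure (as defined in Section 9.4.1".
- **Suspension rule.** Section 12.4 cites Section 9.4.1, treats a true rate of 5% or more as excessive, and asks for a one-sided 80% lower confidence limit above that level. Table 3 turns this into "2 failures of first 16 pts or fewer, 3/17-30, 4/31-46, 5/47-50".

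On eligibility, Section 7.1 requires remission for the acute leukemias, for example "Acute myelogenous leukemia (AML) in first or subsequent morphologic complete remission". Criterion 2c admits "Myelodysplastic syndrome (MDS), chronic myelomonocytic leukemia (CMML), myeloproliferative disorder (MPD) including myeloid metaplasia and myelofibrosis" on a marrow blast count below 10%. Criterion 2d admits CML in chronic phase.

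On timing, footnote q to the Schedule of Assessments leaves disease evaluation to institutional guidelines but requires a marrow "at baseline, and at time intervals close to Days 100, 180 and 365".

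Section 8.10.2, for the Expansion Phase, uses a different formulation: "If a subject does not demonstrate evidence of myeloid engraftment by Day 28". It sets no remission condition.

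**The concern.** A graft failure count should capture transplanted subjects whose neutrophils do not recover. This definition adds a disease-status condition that criteria 2c and 2d do not require at entry. A subject with myelofibrosis who was never in remission and has no neutrophil recovery at Day 28 does not meet the definition as written. For AML and ALL, remission holds at entry, but no required visit confirms it around Day 28.

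The affected diagnoses are not marginal to the plan. MDS and MPD including CMML are two of the four diagnosis levels listed for adjustment in the primary model (Section 12.3.1), and SAP Section 2.4 names MDS and MPD in the study population.

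At stake is the reported incidence of a primary safety outcome and the working of one of three suspension triggers. The SAP does not settle the matter: it lists graft failure as an endpoint but neither defines nor tabulates it.

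**Working it through.** **Inputs.** From the protocol: the 5% limit and the one-sided 80% criterion (Section 12.4), the Table 3 boundary, and the Table 4 values for true rates of .02 and .12. Assumed, because the documents give no diagnosis mix: the share f of true non-engraftments left uncounted, taken as 20% to 50%.

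**Step 1: reproduce Table 3.** The exact (Clopper-Pearson) lower limit for k failures in n patients is the 20th percentile of a Beta(k, n − k + 1) distribution.

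- 2 failures: 5.18% at n = 16, 4.88% at n = 17
- 3 failures: 5.16% at n = 30, 4.99% at n = 31
- 4 failures: 5.03% at n = 46, 4.93% at n = 47

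The limit drops below 5% exactly where Table 3 raises the count. At the accrual cap, 5 of 50 gives 6.24%. The printed boundary is reproduced.

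**Step 2: reproduce Table 4.** Apply the boundary after every patient and add up the binomial probability of first reaching it. For 10 patients at .12 this can be done by hand: 1 − .88^10 − 10 × .12 × .88^9 = 1 − .2785 − .3798 = .342.

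| True rate | Patients | Table 4 | Recomputed |
|---|---|---|---|
| .02 | 10 / 25 / 45 | .02 / .04 / .05 | .016 / .043 / .053 |
| .12 | 10 / 25 / 45 | .36 / .68 / .88 | .342 / .683 / .859 |

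Agreement is within about 2 points, which simulation error could explain. Table 4 is therefore sound for the event that Table 3 counts.

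**Step 3: leave a share f uncounted, at a true non-engraftment rate of .12.**

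(a) All patients stay in the denominator. The counted rate is .12 × (1 − f), and the same calculation is run to 45 patients.

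(b) Uncounted subjects also leave the denominator. The rate stays at .12, but the number of patients falls to 45 × (1 − f). This is 36, 31.5, 27 and 22.5; the two fractions are taken as 31 and 22.

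| f | Counted rate in (a) | (a) by 25 | (a) by 45 | (b) by 45 |
|---|---|---|---|---|
| 0 | .120 | .68 | .86 | .86 |
| 20% | .096 | .54 | .73 | .79 |
| 30% | .084 | .46 | .64 | .76 |
| 40% | .072 | .38 | .53 | .72 |
| 50% | .060 | .29 | .41 | .64 |

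Table 3 says only that it counts patients, so the documents do not decide between (a) and (b).

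**Step 4: a case that needs no assumption about mix.** Two of the first 16 patients do not engraft, and one of them has myelofibrosis never in remission. Counting both gives 2 of 16 and suspends the study. Counting literally gives 1 of 16, or 1 of 15 if the subject also leaves the denominator. Neither reaches the boundary.

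**The case against.** The strongest reply is that survival in remission can mean survival without relapse or progression after transplant. On that reading the affected diagnoses are counted and only a clarification is needed. The reading is reasonable, but the protocol does not state it. Two readings that give different counts for a suspension rule are themselves a reason to fix the wording.

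A reader might infer more than the documents support, in five ways.

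- **That Table 4 overstates the rule's sensitivity.** It does not. Section 12.4 ties the monitored rate to the Section 9.4.1 event, and Table 4 holds for that event.
- **That many subjects are affected.** No diagnosis mix is given, and AML and ALL must be in remission at entry. Treating everyone enrolled under 2c or 2d as uncounted would be an upper bound.
- **That remission is never assessed before Day 100.** There is a screening assessment, unscheduled ones are allowed, and institutional practice may add others. The contents list a Section 9.3.1 on tumor assessment, but its text is not in the supplied protocol. The supportable statement is that the supplied text requires no post-transplant assessment before about Day 100.
- **That one subject can stop under the Day 28 rule and also be missed from the DLT count.** The Day 28 rule belongs to the Expansion Phase (Section 8.10.2), whereas DLTs are counted in the run-in. There the SRC also weighs all the safety data.
- **That non-engraftment disappears from view.** Time to engraftment is a safety assessment (Section 9.4). SAP Section 9.3 and Listing 16.2.6.1 report it without a remission condition, and the SRC monitors safety throughout. None of these, however, is specified as feeding the Table 3 count.

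**Conclusion.** The point holds as a gap in the definition, not as an error in the tables. Read literally, Section 9.4.1 leaves out non-engraftment in subjects who may enter without remission. Both the primary safety endpoint and the 5% suspension rule inherit that omission.

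The existence of the gap follows from the text alone. Its size does not: the loss by 45 patients, from .86 to .73-.41 or to .79-.64, depends on an assumed uncounted share of 20-50%, a true rate of 12%, and the choice of denominator. With triggers as low as 2 or 3 events, a single case can matter whatever the mix. This is an inexpensive improvement that should be made.

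**What to change.** For the safety endpoint and the Table 3 count, define graft failure as no myeloid engraftment in a subject alive at least 28 days after transplant without documented relapse or progression of the malignancy. A case then counts unless relapse or progression is on record, so no new Day 28 marrow is needed. State beside Table 3 which patients form the denominator, so that it matches the definition, and add a graft failure table to the SAP.

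The cost is one sentence in Section 9.4.1, a note to Table 3 and one SAP table. Neutrophil recovery dates (SAP Section 9.3) and relapse or progression (SAP Section 8.4) are already collected. The downside is that the observed rate, and so the chance of an SRC review, may be somewhat higher against an unchanged 5% limit. That limit rests on a cited study whose own definition is not shown in the protocol, so the sponsor should confirm that the two are comparable.

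Section 6.1.1 refers to Section 9.4.1, and Section 8.10.2 uses both the DLT criteria and its own Day 28 non-engraftment wording. The sponsor should reconcile these passages with the revised definition. No view is taken here on those treatment rules.
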